BRIGHtMIND is a randomised controlled trial and compares two transcranial magnetic stimulation (TMS) methods for treatment-resistant depression (TRD): standard repetitive TMS (rTMS) and connectivity-guided intermittent theta-burst stimulation (cgiTBS). The overall protocol for trial has been published (Morriss et al., 2020), modified with the COVID-19 pandemic (Pszczolkowski et al., 2022). In brief, the trial protocol includes clinical, psychometric and cognitive assessment and multimodal brain imaging at 3T at baseline and 16 weeks following rTMS or cgiTBS (20 sessions spanning across 4-6 weeks). Both types of TMS are delivered to the left dorsolateral prefrontal cortex (DLPFC), a key component of the “executive control network” (ECN) of brain areas. The selection of the stimulation target site was imaging-based for both treatment arms with different approaches. T1-weighted structural MRI was used to find the grey matter voxel the nearest to the “F3” international 10-20 system scalp location for the rTMS arm, while the target for the cgiTBS arm was decided from the structural and resting-state functional MRI, by finding the grey matter voxel in the left ECN, which shows the greatest “effective connectivity” (EC) from the right anterior insula.

All participants underwent MRI for neuronavigation at all four scanning sites (Nottingham, Newcastle, London and Manchester), and a subset of participants (those recruited for scanning at Nottingham or Newcastle) was also enrolled into the mechanistic proton MR spectroscopy (MRS) substudy, whereby GABA-edited MRS was acquired over the DLPFC at baseline and 16-weeks follow-up. Here, we summarise the rationale and hypotheses and describe processing details and changes from the original protocol plan and document the statistical analysis plan that will be followed for the MRS substudy.

Compared to the published protocol (Pszczolkowski et al., 2022), the MRS processing pipeline has been changed due to a compatibility issue in spectra processing pipeline across MRI vendors. Originally, we proposed to use an in-house MATLAB processing pipeline and LCModel to quantify metabolites based on experience with the main MRS platform. However, due to implementation challenges on other platforms and based on favourable in-house comparison between pipelines we decided to switch to GANNET, a MATLAB package to process spectra and quantify metabolites, which is in line with recent recommendations based on a thorough validation study across multi-sites and different vendors (Mikkelsen et al., 2017). We will, however, still report the LCModel derived results from a single-site, single vendor protocol for interest.

Glutamate and GABA are major excitatory and inhibitory neurotransmitters respectively and can be detected noninvasively detectable by MRS. However, MRS detectable glutamate and GABA levels are not direct read-outs of the respective neurotransmitter pool but there is strong supportive evidence that GABA levels co-vary with the extent of inhibitory activity while glutamate may index increased metabolic or excitatory activity. Due to the inability to separate glutamate from glutamine, commonly Glx (the estimated sum of glutamate and glutamine) is reported. GABA/Glx in particular

is an increasingly used index of the inhibitory/excitatory ratio which is considered to be robust in healthy brains.

In chronic stress and depression, there is well-documented impaired function of GABAergic and glutamatergic neurons in the PFC and hippocampus with some suggestion that GABA dysfunction may be the primary pathogenic mechanism (Duman et al., 2019). In people with depression, decreased frontal GABA_B receptors and reduced GABA levels in the plasma, cortical and limbic brain areas were reported in preclinical and clinical studies (for a review, see Duman et al., 2019). Alterations of GABAergic transmission have long been considered as putative pathomechanism and treatment target in affective disorders (Kalueff & Nutt, 2007; Lloyd et al., 1989; Möhler, 2012). A recent meta-analysis of Glx MRS studies in depression (Moriguchi et al., 2019) shows overall reduction that medial prefrontal Glx/glutamate with some variation and possible link to medication state. Despite some reports of increased Glx, the overall parallel reduction of Glx and GABA cautions against use of GABA/Glx as marker of inhibitory/excitatory balance in people with depressions, which may explain the negative finding reported by Narayan et al., (2022) as they found no changes of medial prefrontal GABA/Glx after 8 weeks of escitalopram treatment, and no association with change in depression scores. By contrast, there is suggestive evidence that antidepressants and in particular short-acting agents like ketamine may restore a balanced GABAergic and glutamatergic neurotransmission as part of the antidepressant treatment efficacy (Silberbauer et al., 2020; Stone et al., 2012).

TMS related neurochemical changes were reported in few studies focusing on GABAergic or glutamatergic neurochemicals, with variable findings based on typically small sample sizes and differing TMS and MRS protocols in healthy controls and patients (Gonsalves et al., 2022). In rTMS responders who were TRD patients, GABA levels in the dorsolateral prefrontal cortex increased after rTMS treatment while no trend was observed in the non-responders (Levitt et al., 2019). A recent small MRSI study in TRD reported localised mPFC Glx increases after iTBS but no GABA changes (Spurny-Dworak et al., 2022). There is however some existing literature describing that frontal glutamatergic metabolites and GABA increases after high frequency left DLPFC rTMS in association with clinical improvement. Conversely, a recent study shows an increase of mPFC GABA post iTBS in acute bipolar depression that was unrelated to clinical improvement (Diederichs et al., 2021). Also, in our unreported MRS substudy of the pilot cgtTBS study in TRD (Iwabuchi et al., 2019) we found no GABA changes at 3 months post iTBS, but some suggestion of predictive power of baseline prefrontal GABA for HDRS-17 and Beck Depression Inventory (BDI) scores at 3 months. Moreover, GABA and HDRS-17 change between baseline and 3 months was moderately correlated suggesting an inverse relationship with clinical improvement. The negative relationship between GABA and HDRS-17 changes suggests that GABA increase may result in the clinical improvement in depression. Our pilot study also showed acute reduction of the ratio of prefrontal GABA/Glx after a single session of 3000 TBS pulses over the left DLPFC in healthy volunteers (Iwabuchi et al., 2017). The observed acute change pattern is well in line with the expected excitatory nature of iTBS but it is unknown whether chronic GABA/Glx changes would occur in healthy volunteers nor are there reports on acute changes in people with depression. Differences are however expected in neurobiological effects between healthy brains and patients with depression and between acute treatment effects and chronic neuroplastic changes with further likely differences between brain regions as well as recognised inter-individual variability ascribed to meta-plasticity (Kinjo et al., 2021). Taken together, there is strong evidence for impaired prefrontal GABAergic and glutamatergic neurotransmitter systems in depression, but conflicting evidence whether reversal of these neurochemical alterations (and in which brain regions) by TMS may be an important mechanism of its antidepressant efficacy.

Role of this analysis plan

To better understand the mechanism of action of TMS, and of any putative benefit of cgitBS over standard repetitive TMS, we will examine a set of hypotheses derived from prior literature. Here, we describe the spectroscopic processing and statistical analysis plan.

The main study rationale is to assess whether clinical response to treatment is associated with GABA changes in the DLPFC.

Definitions of measures

- *Clinical improvement*
Mean change in depression measure from baseline (17-item HDRS total score as primary measure); changes from baseline in BDI, QIDS-SR-16, PHQ-9 and GAD-7 will be used for exploratory analyses only)
- *Treatment response*
Reduction in depression measure (17-item HDRS total score) of 50% or greater compared to baseline
- *Metabolite ratios*

GABA levels relative to Cr (GABA+/Cr), Glx levels relative to Cr (Glx/Cr) and GABA levels relative to Glx (GABA+/Glx as no macromolecule suppression). Glx and Cr will be estimated from non-edited spectra.

Primary hypotheses

1. Changes in depression symptoms on 17-item HDRS (16 weeks versus baseline) will be associated with change in GABA+/Cr between baseline and 16 weeks (post minus pre-treatment) in both treatment groups with increase in GABA+/Cr expected to be associated with decrease of HDRS (improvement).
2. Changes in depression symptoms on 17-item HDRS (26 weeks versus baseline) will be associated with change in GABA+/Cr between baseline and 16 weeks (post minus pre-treatment) in both treatment groups with increase in GABA+/Cr expected to be associated with decrease of HDRS (improvement).
3. Greater clinical improvement on 17-item HDRS (16 and 26-week vs baseline) will be associated with lower GABA+/Cr at baseline across both treatment groups.

Secondary hypotheses

1. GABA+/Cr will be increased after treatment compared to baseline for treatment responders across both treatment groups (a) and (b) GABA+/Cr increase will be higher in responders than in non-responders.
2. GABA+/Cr increase will be higher in cgtTBS compared to rTMS group (all patients).
3. Greater averaged and sustained clinical improvement on 17-item HDRS (averaged over 8,16 26-week follow-up) will be associated with more GABA+/Cr change across both treatment groups.
4. Greater averaged and sustained clinical improvement on 17-item HDRS (averaged over 8, 16 26-week follow-up) will be associated with lower GABA+/Cr at baseline across both treatment groups.
5. Glx/Cr will be increased after treatment compared to baseline for treatment responders across both treatment groups (a), and Glx/Cr increase will be higher in responders than in non-responders (b).
6. Glx/Cr increase will be higher in cgtTBS compared to rTMS group (all patients).
7. Changes in depression symptoms on 17-item HDRS (16 weeks versus baseline, and 26 weeks versus baseline) will be associated with change in Glx/Cr between baseline and 16 weeks (post minus pre-treatment) in both treatment groups.

Exploratory hypotheses:

1. All the above hypotheses will be tested with other measures of depression used in the study to test robustness of findings, namely HDRS-6, BDI, PHQ-9 and QIDS-SR-16
2. GABA+/Glx changes will be associated with clinical outcomes (17-item HDRS at 16 and 26 weeks).
3. GABA+/Cr and Glx/Cr changes correlate with rAI-DLPFC net outflow changes (16 weeks vs baseline).
4. GABA+/Glx is associated with rAI-DLPFC FC and net outflow (baseline and 16 weeks) with stronger association in treatment responders after treatment compared to baseline.

5. Clinical subtypes, especially TRD severity and comorbid anxiety are associated with changes in GABA+/Cr.
6. Treatment response is associated with changes in the association between intrinsic within and between brain network FC metrics and DLPFC GABA+/Cr, Glx/Cr and GABA+/Glx levels.

Required data

- MEGA-PRESS MRS and resting-state functional MRI at baseline and, where available, at 16 weeks
- Treatment group assignment (rTMS or cgtTBS)
- Participant age, sex, and study centre and MRS protocol/platform
- For each participant, whether protocol deviations were submitted on the basis of stimulation sequence or localisation method received
- For each participant, whether there were any changes in medications in BNF Chapter 4 between baseline and 16 weeks (including starting and stopping medications)
- For each participant, whether ECT was delivered between baseline and 16 weeks
- For each participant, whether they started psychotherapy between baseline and 16 weeks
- For each participant, whether any major protocol deviations occurred from baseline to 16 weeks
- 17-item HDRS total score at baseline, 8-week follow-up, 16-week follow-up and 26-week follow-up.
- 6-item HDRS total score at baseline, 8-week follow-up, 16-week follow-up and 26-week follow-up.
- Beck Depression Inventory at baseline, 8-week follow-up, 16-week follow-up and 26-week follow-up
- 16-item self-report Quick Inventory of Depression Symptoms (QIDS-SR-16) at baseline, 8-week follow-up, 16-week follow-up and 26-week follow-up
- 9-item Personal Health Questionnaire (PHQ-9) at baseline, 8-week follow-up, 16-week follow-up and 26-week follow-up
- Total score on the GAD-7 measure of anxiety
- Massachusetts Treatment Resistance category (mild, moderate, severe as defined in trial protocol)

Regions of interest (ROIs) / Voxel of interest (VOI)

- For MRS, a voxel (20x45x30mm) was placed on the left DLPFC based on the individual T1 anatomical image acquired prior to the MRS session.
- Grey Matter (GM), White Matter (WM) and Cerebrospinal fluid (CSF) will be parcellated through GANNET segmentation with SPM12. The GM values will be covariates of no interest in the statistical analysis.

Sensitivity analyses

In order to examine whether quality of MRS affected the results, we will conduct sensitivity analyses to

- assess a potential effect from outliers in voxel position. For this, coverage of anatomical DLPFC (in percent) and overlap with TMS brain target within the individual MRS voxels will inform through the sensitivity analysis.
- assess spectral fitting quality effects. For this, only data with higher quality data fit will be used to repeat primary and secondary hypothesis with $p < 0.1$ results.

Statistical tests

Primary Hypotheses

- The correlation between change in GABA+/Cr between baseline and 16 weeks (post minus pre-treatment) and clinical improvement will be tested by regression with the following covariates for P1 and P2:
 - *Age*
 - *Sex*
 - *Treatment group (rTMS or cgtTMS)*
 - *MGH treatment resistance*
 - *Baseline 17-item HDRS*
 - *Study centre*
 - *MRS platform (scanner/protocol)*
 - *MRS quality (GABA+ fitting error)*

$P < 0.01666$ will be the level considered for statistical significance ($p < 0.05/3$, i.e. 5% significance level with Bonferroni correction for 3 co-primary hypotheses). For missing data (e.g. due to poor spectra quality, participants' absence for the scanning or incompleteness of whole MRS sessions) we will take an available data approach, meaning individuals with enough data for a model will be included in that model's analysis.

- For P3, a mixed effects model will be used with participant as random effect to account for three repeated measures. Each participant will contribute up to 3 repeated outcome measures to the model in addition to the baseline HDRS-17 score. The model will be adjusted for the stratification and minimisation variables: baseline HDRS-17 score, baseline Massachusetts General Hospital Treatment Resistant Depression score, and study centre as part of the covariable detailed above. For missing data, we will take an available data approach, meaning individuals with enough data for a model will be included that model's analysis.

Secondary Hypotheses

Secondary hypotheses S2, S3, S5, S6, S7 will be analysed as above, for S1 and S4 we will use a mixed model

- A Linear mixed model will be used with GABA+/Cr as the dependent variables.
- Independent variables will be the *Treatment* response group, *Time* (pre-and post) and *Treatment type*
- Covariates of no interest include
 - *Age*
 - *Sex*
 - *MGH treatment resistance group*
 - *Study centre*
 - *MRS platform (scanner/protocol)*
 - *MRS quality (GABA+/Glx fitting error respectively)*

We will take an available data approach, meaning individuals with enough data for a model will be included in that model's analysis. For secondary analyses $P < 0.05$ will be considered significant without Bonferroni correction.

The statistical analysis for primary and secondary hypotheses will be performed using a current version of either SPSS, SAS, Stata or R (for graphical illustrations). Diagnostic plots of model residuals, and the results of the Shapiro-Wilk test, will be used to determine whether variable transformations are required.

Exploratory hypotheses

Exploratory tests will be undertaken using current versions of either established advanced image analyses, SPSS, SAS, Stata or R (for graphical illustrations).

Included participants

All trial participants with baseline T1-weighted structural MRI, and MRS passing quality control criteria as detailed later in this document. We will include only participants that received the treatment to which they were assigned (that is, participants without protocol deviations on the basis of stimulation sequence or localisation method used).

Data processing

We originally planned to perform the entire MRS analysis using LCModel but during preprocessing noted that data from only one vendor was compatible for our in-house analysis pipeline. Due to time constraints, we then decided to use GANNET instead. Acquired spectra in the left DLPFC will thus be processed with GANNET MATLAB package (v 3.3.0) with the default setting. MEGA-PRESS origin will be set as 'JHU' in GANNET for Nottingham GE and Newcastle Philips data and 'Phillips' for Nottingham Philips. For completeness we will also report summary results from LCModel based GABA+/Cr estimates. In brief, GANNET processing uses time domain signals that will be frequency and phase corrected by spectral registration. 3-Hz exponential line broadening and zero-filling with a factor of 16 will be applied for filtration. Each pair of spectra (edited – non edited) will be aligned, and edited spectra will be subtracted from non-edited spectra to detect a GABA peak. The processed spectra will be averaged and fit to Gaussian function to the GABA and Glx peak at 3.0 and 3.8 ppm,

respectively. GABA peak will be modelled using a five-parameter Gaussian model (2.19 – 3.55 ppm) and water peak will be modelled using a Gaussian-Lorentzian function. Creatine and N-acetylaspartate will be modelled as two Lorentzians in the non-edited spectra. The integral Cr area in non-edited spectra will be used to calculate GABA+ ratio relative to Cr. Linewidths of water and NAA peak will be reported for quality control.

We are employing the best practice of Glx estimation from MEGA-PRESS or validated equivalence using the GANNET pipeline. Glx acquisitions from edit-off MEGA-PRESS spectra show significantly higher correlation with Glx levels acquired by Point RESolved Spectroscopy (PRESS) than Glx from edit-on MEGA-PRESS spectra (Maddock et al., 2018), hence we aim to measure Glx levels from edit-off spectra. Once the compatibility issue is addressed with our in-house pipeline, measured GABA from edited spectra and Glx and other metabolite levels from non-edited spectra will be reported using our in-house MATLAB pipeline and LCMoDel. All the MRS sequence parameters pinned down for the various acquisitions will be checked, and the sequence specific basis sets will be built in the future for the Glx measurements.

Quality control

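### GABA is tested only as a ratio to creatine, and no planned analysis checks that creatine is stable or unrelated to outcome

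*SAP*

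**What the plan says.** Under Role of this analysis plan, the SAP sets out its purpose: "The main study rationale is to assess whether clinical response to treatment is associated with GABA changes in the DLPFC". Under Definitions of measures, the metabolite measures are "GABA levels relative to Cr (GABA+/Cr), Glx levels relative to Cr (Glx/Cr) and GABA levels relative to Glx".

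- **P1 and P2:** HDRS-17 change at 16 and 26 weeks "will be associated with change in GABA+/Cr between baseline and 16 weeks (post minus pre-treatment) in both treatment groups".
- **P3:** greater improvement "will be associated with lower GABA+/Cr at baseline across both treatment groups".
- **S1-S4:** GABA+/Cr again, by response group, by arm, and against averaged improvement.
- **S5-S7:** Glx/Cr.

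Under Data processing, "The integral Cr area in non-edited spectra will be used to calculate GABA+ ratio relative to Cr". The same section says that the "water peak will be modelled using a Gaussian-Lorentzian function", and Quality control excludes measurements on a water-referenced fit error. Grey matter, white matter and CSF are segmented. Water is therefore available in the processing chain, but it serves as the reference for no endpoint.

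The Sensitivity analyses section has two items: voxel position and spectral fit quality. The supplementary LCModel report is also of GABA+/Cr.

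**The concern.** A ratio to creatine measures GABA only if creatine is constant, or at least unrelated to whatever the ratio is tested against. For P1, P2 and S1-S3 this means creatine change between the two scans. For P3 and S4 it means differences between people in baseline creatine. The plan relies on this assumption and never examines it.

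If creatine fell more in patients who improved, GABA+/Cr would rise with improvement. That is the direction P1 and P2 predict, and it would occur with GABA unchanged. Glx/Cr has the same denominator and would move the same way, so parallel results on the two ratios would not be two separate pieces of evidence. What is at stake is whether a positive result can be described as a GABA result, which is the purpose of the substudy.

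**Working it through.** **1. The plan's own figure.** Statistical tests gives 0.01666 as the primary significance level. 0.05/3 = 0.016667, so it is reproduced. The SAP gives no sample size, SD or effect size; those used below are assumptions.

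**2. Where creatine enters.**

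| Analysis | Measure | Contains creatine? |
|---|---|---|
| P1-P3, S1-S4 | GABA+/Cr | Yes |
| S5-S7 | Glx/Cr | Yes |
| LCModel report | GABA+/Cr | Yes |
| Exploratory hypothesis 2 | GABA+/Glx | No, but does not measure creatine |
| Sensitivity analyses | Voxel position, fit quality | Creatine not examined |

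**3. Ratio arithmetic (no assumption needed).** With GABA and Glx fixed and creatine multiplied by (1 + c), both GABA+/Cr and Glx/Cr change by 1/(1 + c) - 1.

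| Creatine change | Change in GABA+/Cr and in Glx/Cr | Change in GABA+/Glx |
|---|---|---|
| -2% | +2.0% | 0 |
| -5% | +5.3% | 0 |
| -10% | +11.1% | 0 |
| +5% | -4.8% | 0 |

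**4. Size for P1 or P2, under assumptions.** GABA change is unrelated to HDRS change. The SD of log change is 10-15% for GABA and 3-5% for creatine. Creatine change correlates r with HDRS change. n = 100, with 9 covariates: the eight listed for P1 and P2 plus grey matter, each counted as one term.

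The size of the induced correlation is r × SD_Cr / √(SD_GABA² + SD_Cr²). The rejection probability uses Fisher's z with n - 3 - 9 = 88 and a two-sided level of 0.05/3 (critical value 2.394).

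Worked case, SDs 10% and 5%, r = 0.5: 0.5 × 0.05 / √(0.0100 + 0.0025) = 0.224. Fisher z = 0.227, and 0.227 × √88 = 2.13. The normal probability below 2.13 - 2.394 = -0.26 is 39.7%.

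| r (creatine, HDRS) | Induced correlation | Chance of p < 0.0167 |
|---|---|---|
| 0 | 0 | 1.7% |
| 0.1 | 0.02-0.04 | 1.9-2.7% |
| 0.2 | 0.04-0.09 | 2.4-6.1% |
| 0.3 | 0.06-0.13 | 3.4-13.0% |
| 0.5 | 0.10-0.22 | 7.1-39.7% |

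At n = 60 the worst cell falls from 39.7% to 21%. The calculation concerns a change-on-change correlation. It gives no figure for P3 or for the group comparisons.

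**5. Cross-check by simulation.** 4,000 runs per cell, unadjusted, SDs of 10% (GABA), 6% (Glx) and 3-5% (creatine), at n = 50, 80 and 120.

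- With creatine unrelated to HDRS, GABA+/Cr rejects in 1.2-1.8% of runs.
- At n = 80 it rejects in 5.3% (creatine SD 3%, r 0.3), 11.3% (5%, 0.3) and 35.1% (5%, 0.5).
- A water-referenced GABA+ outcome stays at 1.1-1.9% in every cell. The simulation gave it no added measurement noise, so this shows protection against creatine, not its precision.
- The shared denominator alone gives the changes in the two creatine ratios a correlation of SD_Cr² / √[(SD_GABA² + SD_Cr²)(SD_Glx² + SD_Cr²)], which is 0.13 at a creatine SD of 3% and 0.29 at 5%.

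**The case against.** Creatine referencing is conventional. The SAP labels its measures openly as ratios, and every primary and secondary hypothesis names the ratio it tests. Nothing in the SAP suggests that creatine responds to TMS or tracks HDRS; if it does not, the error rate is nominal. These points stand. They are why GABA+/Cr should remain primary and why the table must start at r = 0.

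Exploratory hypothesis 2 also gives a partial creatine-free check, because a pure creatine shift would leave GABA+/Glx flat. This stands in part. The SAP does not designate it as such a check, and its background cautions against that ratio as a marker of inhibitory/excitatory balance in depression. A flat GABA+/Glx with both creatine ratios raised fits a fall in creatine and also fits a true parallel rise in GABA and Glx. The background cites reports of increases in both after left DLPFC rTMS.

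The covariates for grey matter, centre and platform may absorb some baseline creatine variation between people and scanners. They do not remove a creatine change that follows clinical change. Data processing also foresees reporting other metabolite levels, but only once the in-house pipeline works, and with no test.

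A reader might infer that a significant P1, P2 or P3 could never be attributed to GABA, or that the SAP treats Glx/Cr as confirmation of GABA+/Cr. The documents support neither. The attribution is untested, not refuted, and S5-S7 are stated as separate secondary hypotheses.

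**Conclusion.** The concern holds as a gap in the check on a key assumption. The primary endpoint is not in error. P1-P3 and S1-S4 address GABA only through GABA+/Cr, and no planned analysis would show whether creatine contributed to a result. The ratio arithmetic is certain. The size of any bias is conditional: for P1 or P2 it is nil at zero creatine-HDRS correlation, small (about 2-6% against 1.7%) at 0.1-0.2, and 3-40% at 0.3-0.5, with the SDs and n = 100 all assumed.

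A reader might take 40% as the expected error rate. It is the corner where the GABA SD is lowest and the creatine SD and correlation are highest, and no document supports a correlation of that size. Nor do the documents show that creatine moves at all. The change is worth making because it is cheap and fixes the alternative reference before results are seen.

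**What to change.** Keep GABA+/Cr as the primary measure. Add to Sensitivity analyses:

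- (a) P1-P3 and S1-S4 repeated with tissue-corrected, water-referenced GABA+ from the same GANNET fit;
- (b) the same models with Cr/water as the metabolite.

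Report estimates and confidence intervals beside the GABA+/Cr results. State that a result will be described as a change or difference in the ratio, not in GABA, where the water-referenced GABA+ estimate does not support it. A pass/fail rule is not advised: without thresholds it is undefined, and a non-significant Cr/water result does not show that creatine had no effect.

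Do not extend the water-referenced repeat to Glx unless Glx is taken from the edit-off spectra. Definitions of measures specifies non-edited spectra for Glx, whereas Data processing describes the GANNET Glx peak fit after subtraction. A repeat from that fit would change the measure as well as the reference. For S5-S7, use the Cr/water result to interpret Glx/Cr.

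The cost is a few lines of SAP text and re-running models already specified, on signals already fitted and tissue already segmented. Water referencing and tissue correction add noise of their own, so these belong in the sensitivity analyses and should not replace the primary.

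### Exploratory hypothesis 6 brings clinical outcome in only through the 50% HDRS-17 responder cut, with no version using continuous HDRS-17 change

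*SAP*

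**What the plan says.** Under Definitions of measures the SAP separates two outcome concepts. Clinical improvement is a change score: "Mean change in depression measure from baseline (17-item HDRS total score as primary measure". Treatment response is a dichotomy: "Reduction in depression measure (17-item HDRS total score) of 50% or greater compared to baseline".

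Under Exploratory hypotheses, number 6 uses the second concept: "Treatment response is associated with changes in the association between intrinsic within and between brain network FC metrics and DLPFC GABA+/Cr, Glx/Cr and GABA+/Glx levels". Number 4 has two parts. The first relates GABA+/Glx to rAI-DLPFC connectivity and net outflow at baseline and week 16, with no clinical outcome. The second adds "with stronger association in treatment responders after treatment compared to baseline".

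The continuous scale is at hand. Required data lists "17-item HDRS total score at baseline, 8-week follow-up, 16-week follow-up and 26-week follow-up". The plan uses HDRS-17 as a score or change in primary hypotheses 1 to 3, secondary hypotheses 3, 4 and 7, and exploratory hypothesis 2. Primary hypothesis 1, for example, reads "Changes in depression symptoms on 17-item HDRS (16 weeks versus baseline) will be associated with change in GABA+/Cr".

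For the exploratory tests, the Statistical tests section names software only. It gives no model.

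**The concern.** Elsewhere the plan pairs a responder comparison with a full-scale one. The responder contrast in GABA+/Cr change (secondary 1b) sits beside primary 1, and the one in Glx/Cr change (secondary 5b) sits beside secondary 7. Exploratory 6 has no such partner, so the cut is the only way in which outcome enters.

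Taken literally, a patient with a 49% fall in HDRS-17 is grouped with one who worsened and separated from one with a 51% fall. Exploratory 6 also asks a moderation question: whether a connectivity-metabolite association changes differently according to outcome. Such tests usually have little power to spare. If the true relation is graded, a null from the dichotomised test would say little, while the same data on the full scale could say more.

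**Working it through.** **Step 1. Is there a continuous version anywhere?** The candidates are:

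- Exploratory 1: "All the above hypotheses will be tested with other measures of depression used in the study to test robustness of findings". It covers the hypotheses listed above it, that is, the primary and secondary ones. It also changes the depression scale, not the cut.
- Exploratory 2: relates GABA+/Glx change to HDRS-17, without connectivity.
- Exploratory 3: relates metabolite change to net outflow change, without a clinical outcome.
- Statistical tests, Exploratory hypotheses: software only.

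None supplies it.

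**Step 2. Inputs for the size.** The SAP states no responder share, sample size or power for this hypothesis, so there is no figure of its own to reproduce. Assumed: responder share p between 25% and 50%, and a near-normal HDRS-17 change.

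**Step 3. Information kept by the cut if the effect is linear.** For a normal variable cut at upper share p,

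RE = φ(z)² / [p(1 − p)], where z is the normal quantile at 1 − p.

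- p = 0.50: z = 0, φ = 0.3989, RE = 0.1592 / 0.25 = 0.637, a loss of 36%.
- p = 0.25: z = 0.674, φ = 0.3178, RE = 0.1010 / 0.1875 = 0.539, a loss of 46%.

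The number of participants needed for equal power rises by 1/RE, that is, 1.57-fold and 1.86-fold. Under normality and linearity 36% is the smallest loss at any share. At p = 0.15 the loss is 57%.

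A large-sample simulation of a two-way moderation term gave a loss of 38% (p = 0.50) to 48% (p = 0.25) with a normal moderator. With an HDRS-like variable cut at a 50% reduction (assumed baseline about 23, SD 4; change SD 7) it gave 39% to 50%.

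**Step 4. What this means for power, as illustration only.** Assume a standardised interaction of 0.3, N = 100 and two-sided 5%. Power is Φ(0.3√(N·RE) − 1.96).

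- Continuous: Φ(3.00 − 1.96) = 85%.
- Cut, p = 0.50: Φ(2.39 − 1.96) = 67%.
- Cut, p = 0.25: Φ(2.20 − 1.96) = 60%.

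**Step 5. What if the effect is a step?** RE is the squared correlation between the continuous variable and its cut version, so it works both ways. If the effect depends only on being a responder, the continuous analysis keeps 64% or 54% and the cut keeps everything. Simulated power at interaction 0.3 and n = 80, over responder shares of 25% to 50%:

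| True shape | Continuous | Cut |
|---|---|---|
| Linear | 67–71% | 42–53% |
| Step at the responder threshold | 46–52% | 71–72% |

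The simulations use a two-way term without time, repeated measures or covariates. They compare efficiency. They do not give the power of the three-way model proposed below.

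**The case against.** The strongest reply is that the responder form is a reasonable scientific choice. The SAP's background cites a study in treatment-resistant depression in which DLPFC GABA rose in rTMS responders and showed no trend in non-responders, and the SAP says its hypotheses derive from prior literature. If that pattern carries over to connectivity, the cut is the better test, as Step 5 shows. This stands as a reason to keep the responder contrast. It does not justify having that contrast alone, because the same background also reports a moderate graded correlation between GABA change and HDRS-17 change in the group's own pilot.

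A reader might infer that the plan throws away 36–46% of the information as a matter of fact. The document does not support that: the figure depends on an assumed responder share, normality and linearity.

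A reader might also infer that exploratory 4 has the same defect throughout. It does not. Its first clause uses no outcome. Its second reads most naturally as a before/after contrast within responders, where response selects a subgroup and is not a moderator. A continuous three-way term would answer a different question there.

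Finally, these hypotheses are exploratory and no model is given for them, so nothing bars a continuous analysis. That limits the stakes, but it still leaves the continuous version unplanned.

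**Conclusion.** The point holds for exploratory 6: by the SAP's own definitions, outcome enters only as the 50% cut, and no continuous counterpart is planned. The loss is about 36% of the information at a 50% responder share and about 46% at 25%, provided that HDRS-17 change is near normal and the effect roughly linear in it. The responder shares are assumptions. A clearly bimodal outcome would shrink the loss, and a responder-only effect would reverse the comparison. For exploratory 4 the point reaches only the responder clause, and only as a case for a companion analysis. This is a minor improvement to exploratory work: no primary or secondary conclusion depends on it.

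**What to change.** For exploratory 6, state as the main form a model for the metabolite ratio with the FC metric × HDRS-17 change (baseline to week 16) × time term, all lower-order terms, and baseline HDRS-17. Keep the responder split alongside as a supporting analysis, so that a step-shaped effect is not missed. State a linearity check for this model, because the residual plots already planned are described for the primary and secondary hypotheses only.

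For exploratory 4, add the same continuous term, for both FC and net outflow, as a companion to the responder clause. Leave the within-responder before/after contrast in place.

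The definition of treatment response fixes no assessment week, so the week should also be named for the responder split.

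The cost is a few lines in the SAP, one extra exploratory term per analysis, and a result stated per HDRS-17 point. No new data are needed.
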